2.7 Supplies

Please note: All hard-copy forms will be printed and available prior to data collection activities. All other necessary materials will be arranged as needed.

The fieldworker will be responsible for all assets and supplies issued to them at the start of the study. If for any reason they foresee there will be a shortage of documents or supplies, it is their responsibility to inform the Project Coordinator in a reasonable timeframe. If this does not occur, procurement of supplies will unfortunately take longer to obtain which will have a detrimental effect on the daily functionality of the study.

CHAPTER 3: PROTECTION OF HUMAN SUBJECTS

3 Introduction

Protecting the rights and confidentiality of the participants in the MaRISA study is of utmost importance. This chapter will briefly review participants' rights and the commitments to participants that all staff must make, data security issues, and professional ethics.

2.1. Ensuring Participants' Rights, Privacy, and Confidentiality

3.1.1 Participants' Rights

Basic human rights must be respected and maintained by a research organization and all who are involved in its activities. The protection of rights and confidentiality has always been especially critical in studies focused on substance use, where exposure of past or current abuse or addiction can have social, economic, and legal consequences. MaRISA's research procedures are designed to protect individual rights and to comply with all applicable laws and ethical principles. Among the rights that must be protected are:

- *The right to accurate representation:*
 - Requires honesty in dealing with participants and provision of completely accurate information about the study.
- *The right of informed consent:*
 - Requires that a participant be given adequate information to make an informed decision about participation.
- *The right to refuse:*
 - Requires that an individual be fully informed of his/her right to decline to participate, to withdraw, or to refuse to answer any question.
- *The right of privacy:*
 - Requires guarantees against invasion of privacy as well as specific protection as specified in the South African Protection of Personal Information Act of 2013.

These rights are extremely important to us as individuals and as professionals engaged in applied research. All SAMRC studies must develop specific written plans for conducting research with human subjects. Research staff must also operate under the supervision of committees for the protection of human subjects to ensure that they do not violate these rights.

In research involving follow-ups and contacts, it is necessary to collect names, addresses, and other personal information from participants for future follow-ups. A great deal of information collected from participants pose a risk to participants, especially if their use of substances is not known to others. It is extremely important that the data collected be kept confidential.

3.1.2 Project Staff Commitment

The staff member collecting data directly from a participant presents perhaps the greatest risk to a participant's privacy. As in all our research, we are very concerned about this risk and take several steps to ensure that problems do not occur. All project staff are required to sign the **MaRISA Staff Agreement of Confidentiality form**, depending on their project roles and responsibilities. These pledges serve to reinforce the seriousness of this aspect of the study. The confidentiality agreement states that project staff members are prohibited from revealing information obtained from study participants. The agreement also states the consequences for staff revealing this information.

CHAPTER 4: QUALITY ASSURANCE & DATA MANAGEMENT

3. Introduction

It is really important that we collect the correct data (information), in the correct way. In this chapter, we will describe the types of data that we are collecting, give you tips on how to collect good data and also how to correct data which has been collected in error.

Data will be held in a confidential and secure manner as outlined in the Data Management Plan. All data will be entered into REDCap, a password-protected data collection and management system that will have built-in checks for consistency and completeness. Electronic data entered in REDCap will be downloaded to the internal RTI project share weekly. All data are kept on password-protected servers. The PI and Data Manager will be responsible for reviewing and cleaning the data and preparing weekly reports during data collection, with assistance and guidance from RTI Co-Is. All data, including forms with personally identifiable information (PII) such as locator forms and consent forms, will be kept on password-protected servers. South African investigators and staff will have full access to the data. All collected hard-copy data will be stored in double-locked steel cabinets only accessible by the Site-PI, Project Coordinator and the two fieldworkers. All data will be scanned and uploaded to REDCap for ease of access and data analysis purposes.

Data Quality Control (QC) and Quality Assurance (QA)

Quality assurance systems will be put in place to ensure that the data are cleaned and accurately transmitted, organized, and properly managed. With participants' permission, the Site-PI/Project Coordinator will observe remotely 20% of baseline and follow-up appointments and will document feedback.

Correction Process

Once an issue has been identified in the QA or QC findings, it will be discussed at the weekly site check-in meetings. The root cause of a recurrent problem will be identified, and follow-up actions will be taken to correct the problem based on the input from the RTI and SAMRC staff. These actions may include but are not limited to, changing a process or revisions of project forms, training, or reassignments of tasks. For more serious issues such as protocol violations and breach of project participant confidentiality, the Co-Is will be notified immediately and will work with the field staff to ensure that corrective actions are taken in a timely manner. Based on the severity of the issues identified, the PIs will immediately report the issue to the PO, DSMB Chair and institutional review board of record (SAMRC Ethics Committee), who will determine further recommendations.

Table 1: Corrective Action Reporting Process

Step	Description	Responsible Person
1	Identify the issue (protocol violation, breach of confidentiality, data issue (such as entry, missing etc.))	Project Coordinator and Fieldworkers
2	Report oversight, error or issue to PI or Co-Investigator (Co-I)	Project Coordinator
3	Recognize impact of issue	PIs
4	Investigate cause	PIs
5	Recommend corrective action	PIs
6	Implement corrective action	All staff
7	Notify PO, DSMB Chair and SAMRC Ethics Committee within 48 hours as needed.	PIs

Potential Improvements

Identifying and implementing potential improvement of project protocols will be an ongoing process that will be integrated into the routine planning, management, and implementation project processes. It is the responsibility and standard practice of all project staff to identify and appropriately communicate opportunities for quality improvement to the PIs. These improvements will be documented, and ethics approvals will be included in the yearly progress reports.

3.1. Data collection issues and solutions

Here are a few common issues that may come up during data collection or during a session:

- At the beginning of the assessment, remind the participant how long the assessment will take to complete. Make sure they can stay for that length of time it takes to complete the assessment. Do not begin the assessment if they cannot stay for the entire time it will take- rather reschedule the appointment.
- If you see that a participant is confused about a question or task, stop and ask them if they understand. If you are still not sure if they understand or not, ask them to explain the question to you in their own words.
- If a participant says one thing for one question, and then answers completely differently for another question on the same topic, stop and try to see if the person has understood you. If necessary, go back to the previous question and check their answer.
- At certain times, participants may become less willing to answer questions, or they may seem to just be giving you any answer to finish quickly. Stop the interview and ask the participant if they are alright. Sometimes this is because a participant is upset about something. Sometimes the person is in a rush to leave, or they are hungry or thirsty. Ask them if they would like a break to eat their snacks, take medication or use the bathroom. Let them know how much longer the session will be.
- If at any time you are worried that a participant is not well, alert the medical staff straight away. The participant's medical care is not your responsibility at all. Ask

for help if you are concerned. The following symptoms or signs in participants should be reported:

- a. feeling faint or dizzy
- b. complaining of pain, especially chest pain or a severe headache
- c. sudden weakness
- d. slurred speech
- e. confusion and becomes unable to understand the questions.
- f. any type of sudden bleeding or going into labor
- g. anything else that worries you.

3.2. Entering data on REDCap and filling in paper forms

Data Entry on REDCap Mobile App

- Ensure that the project has been downloaded to the tablets prior to data collection. This may take some time and requires an internet connection.
- After downloading the project, click Collect Data. Select an instrument and click "Create Record" to create a new record or click on an existing record and enter data as usual (following questionnaire flow). Check that each record has been saved and completed. All collected data must be sent to the server at the end of the day. Uploading data requires internet connection. Click "Send Data to Server" and then click "Begin Send button" to send data.
- Before turning off the tablet, please ensure that the data upload is complete. If an error occurs, please email Data Manager for further instructions.
- To ensure that project modifications are current in the app, click "Refresh Setup and Data." This will erase all previous data from the tablet and replace it with everything from the REDCap online server. ((** THIS SHOULD ONLY BE DONE AFTER ALL DATA HAVE BEEN SENT TO THE REDCAP ONLINE SERVER, OTHERWISE ALL DATA COLLECTED ON THE TABLET WILL BE DELETED**)).

If entering data directly on REDCap database

Each fieldworker will use their own username/password or assigned username and password while utilizing REDCap. When entering data, double check Records for duplicates and ensure all forms are completed.

3.3. Submitting collected field data

Should you need to use paper forms to ask the screening questions, baseline or follow-up assessments, you should submit these to the Project Coordinator at the first opportunity. We ask that you fill in the date of the data collection, date when you submitted the forms and which data was collected (screener, baseline assessment, etc.).

3.4. Receiving data queries

Sometimes you will receive a message from the Data Manager, asking about a certain participant or a certain question. This happens in every study, so do not be worried. This may be easy for you to answer straight away, such as giving the correct spelling of a name, or you may need to contact the person (by phone or in person) to verify the information. We need to make sure that all our data are accurate.

3.5. Keeping data safe

All the data we collect for MaRISA, whether digitally (on REDCap) or on hard copies, should be kept safe at all times. Our data include participants' phone numbers, locator information, details of their physical health or that of their babies, consent forms and any other information we collect as part of the study.

3.5.1. Maintaining participant confidentiality

MaRISA data should not be shown to anyone outside of MaRISA. In the same way, none of us should talk about any of the data with anyone not involved in MaRISA, including the clinic/healthcare staff. This is called maintaining participant confidentiality. Each of us will sign a confidentiality agreement before we start the study. Should the clinic staff, a participant's family member or another participant ask you for any information on a study participant, advise them that you may not give them this information as it is confidential. Clinic staff may know that a participant is part of the study, but beyond that we will not be sharing any study details with them. Should they keep asking, please give them the telephone numbers of the Project Coordinator or Site PI to further discuss the matter with them.

3.5.2. Storing our data safely

Once we have collected the data, all the data should be stored safely.

The participant folders should be kept locked away in the filing cabinet, even if you are still busy at the clinic/healthcare facility. You should only have the folders out that you are busy with, and you should never go and have tea, or walk away, leaving any folders, supplies or valuables outside the cabinet. This also applies to any other forms or papers related to MaRISA. If you are not busy on the tablet, please also keep it in the locked cabinet and leave the tablet in the filing cabinet at the end of your shift.

Remember: Any hardcopy forms with patient names or contact details will be stored in the CONTACT folder. All other hardcopy forms will go into the EVERYDAY folder. Each of these files will be kept in separate drawers in the stainless-steel cabinets.

CHAPTER 5: STUDY PROCEDURES

4. Introduction and Expectations

Staff should keep in mind that they are patients' first contact with the project. In doing so, the team gives patients their first impression of the project.

How you approach people, your body language, dress code, attitude and what you say will leave a lasting impression on people who are screened for the study and others. These impressions can influence whether people will want to participate or not in the study. Be conscious of the impressions you make and be careful of what you say – try and make people feel comfortable and welcome.

For the pilot testing phase, we aim to recruit 60 (30 pregnant and 30 post-partum) women for the two healthcare facilities. Both the pregnant and post-partum women need to report that they are using alcohol. Fieldworkers will conduct the baseline assessment, 6-week follow-up assessment, and the 3month follow-up assessment.

5.1 Pilot: Recruitment Procedure

Much of the success of screening potential study participants will result from exercising good judgment and maintaining sensitivity toward the people you speak to. Staff members who have been chosen to work on MaRISA have two important qualities:

- (1) They are capable of working in the healthcare facility and know the surrounding community, and
- (2) They have good instincts as to the best ways to get a response from potential participants. Rely on these instincts but remember that a degree of assertiveness is essential to doing the job well.

It is important to recruit women into the study who seem interested and have a notable level of **readiness to change**, as perceived by the potential participant's verbal and nonverbal communication. Recruiting interested and motivated women into the study increases the likelihood that they will be engaged and committed to completing all steps of the study. **We want participants who are willing and able to come to all**

their appointments. It is therefore important to check whether they have the time and ability to commit to being in the study for the duration of the study.

If people hesitate or do not seem that interested, do not put pressure on them to take part! If we recruit people who are not committed to being in the study throughout the whole process, this will negatively affect our follow-up rate.

Additionally, during the screening and consenting process, project staff members have the opportunity to determine whether participants are mentally capable of participating in the study, particularly during the consent process (which will be further explained below).

If potential participants cannot say in their own words what the study is asking of them during the consent process, they should not be enrolled into the study.

5.2. Screening

Once introductions are made and a patient's cooperation has been secured, complete the participant ID, staff ID, site and date fields on the screener, using the tablet.

- For the pilot phase, we will be using the "Pilot Screener for Pregnant and Post-Partum Women" at the onset of the pilot phase.

Recruitment will be done via clinic referrals, posters, and flyers.

Participant IDs will be according to the following format, it will consist of ten digits with both alphabetic and numerical items, e.g., M_BL0001PR or M_BL0001PP.

Please note: the first alphabetic digit refers to the MaRISA study, an underscore sign separates it from the next 2 alphabetic digits which indicates the site, e.g., Bishop Lavis = M_BL, the next 4 digits indicates how many participants have been enrolled into the study and the last 2 digits indicates whether the participant is currently pregnant or post-partum.

There are types of potentially sensitive information that are requested on the screening questionnaire. It is important to stress the confidential nature of the screener. Reassure them that their identity will never be linked to their responses and that their responses are only used for research purposes. Always remind individuals that their answers will be kept strictly confidential.

Staff ID#: Will be a staff member's Initials.

Site ID#: Bishop Lavis = M_BL; Macassar = 002

To be eligible, women must fulfil in the following criteria, i.e.:

Criterion	Participants
Age	Be ≥ 18
Pregnancy or Post-Partum Status	be pregnant (≤ 28 ges wks) or postpartum (≤ 3 mos)
Alcohol Use	
 have reported alcohol use during the current pregnancy or lactation test positive for alcohol use by urinalysis (i.e., EtG)
Birth Venue (linked to birth outcomes)	plan to complete antenatal care at the current clinic and remain in the area for at least 3 months
Cellphone Status	own a cell phone to receive text messages
Serious Medical Conditions and Suicidal Thoughts	women who report serious medical problems threatening their current pregnancy or report current suicidal thoughts or attempts in the past month are NOT eligible
Other	intend to breastfeed for 6 months

Women who participated in KIIs (the formative phase) or pretesting will not be eligible for pilot testing. Women who reported serious medical problems threatening their current pregnancy or current suicidal thoughts or attempts in the past month will not be eligible and will be provided with necessary referrals.

Table 1: Possible dispositions for not participating or not continuing with participation.

DISPOSITIONS			
	Dispositions based off screening questions		Dispositions before or after screening
2.01	Age < 18 years old	3.01	Not interested (before screening)
2.02	ETG tested negative	3.02	No time

2.03	Refused bio-sample	3.03	eligible, but not interested or refused
2.04	Over 28 weeks preg.	3.04	no reason given
2.05	Over 3 month postpartum	3.05	other
2.06	No alcohol use in current pregnancy or postpartum		

Screening, consenting and baseline and follow-up assessments will be conducted electronically via REDCap. Following consent, we will collect detailed contact information and schedule women for a baseline assessment.

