2.2. Roles and Responsibilities of Staff

2.2.1 Organogram

2.2.2 Project Staffing

There are a variety of staff working on this project.

Project Coordinator: is responsible for assisting the Site-PI with all study related activities and co-ordination, including applications for approval to the Department of Health. They are responsible for overseeing day-to-day activities, ensuring that all study-related materials and incentives are available. They are responsible for data management and will provide support in the reproduction of study-related materials, and assist with literature searches, preparation of slides and other materials for reports, presentations, and publications. They are supervising all field workers, provide training to field workers on recruitment, data collection and tracking procedures. They will conduct quality checking to ensure all data storage SOPs and data collection SOPs are being adhered to. This will include collection of self-report and biological data. They will be responsible for maintaining regulatory (GCP and ethics) oversight, maintenance and stock control of supplies.

Fieldworkers

Will be based at the participating healthcare facilities and MOUs. They will be responsible for conducting screening to identify potential patients who are eligible to participate in the study, consenting eligible patients and enrolling them in the study, scheduling appointments, collecting contact information, conducting the baseline and follow up assessments and tracking participants for study appointments. All of these activities will require the completion of certain paperwork that will be explained in subsequent chapters of this manual. When conducting such activities, staff members must be very conscientious about checking the quality of their own work and ensuring that all interviews are completely and accurately documented using the appropriate forms. Fieldworkers will report directly to the Project Coordinator and indirectly to the Site PI.

Fieldworkers Daily Tasks:

- Maintain confidentiality at all times,
- Be flexible with scheduling appointments (e.g., late afternoon appointments or weekend follow up appointments for assessments),
- Check the quality of own work,
- Check email accounts at least once daily,
- Check project-device messages regularly throughout the day,
- Maintain appointment book
- Keep all supplies in a secure location,
- Report any missing items immediately to the Project Coordinator and

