5.2.1. Alcohol Biological Testing

Please follow the next steps when collecting biological samples.

1. Provide participant with a urine cup to collect a urine sample as part of the screening process.
2. Check the expiration dates when preparing the test.
3. Make sure you have a marker to label the test with the participant's study ID before you start the testing.

Remember, willingness to be tested for alcohol is a requirement for study participation. If a participant has difficulty to pass urine, encourage them to drink some water or juice continue with explanations or completing other forms and to provide the urine sample a bit later. Giving the participant a drink before she starts the appointment will also be helpful.

TEST INSTRUCTIONS

For this study, we will be using an EtG urine test to determine if someone has alcohol in their body. EtG stands for *ethyl glucuronide*, which is a substance produced in the liver when your body processes alcohol. EtG remains present in the body for about one to five days after drinking, depending on how much alcohol a person has drank, using small strips that are dipped in urine. Please use gloves before, during and while cleaning up after the biological testing process. Please conduct the testing as per the steps indicated.

Know What to Expect in 3 Easy Steps

Dip

Dip the dip card into the collected urine sample for 10 sec.

Wait

Re-cap the dip card and lay it on a flat, clean surface.

Read

Read the results at 5 min.

Record results on **MaRISA Specimen Collection Log**.

CLEANING AFTER TESTING

Make sure everything is thrown away appropriately after you have completed all biological testing. Everything used for the testing such as the tray must be wiped down with sanitizer or wipes after conducting biological tests.

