There may be instances where participants are so distressed that you are concerned for their safety and may not be able to continue with the appointment. Remember that we have made it clear in the consent form that there are exceptions to our promise of confidentiality. If participants express the intent to harm themselves or others, or ongoing abuse and/or neglect of children, then we have a duty to report this matter to the proper authorities, e.g., the police, courts or social workers. Field staff will provide information on toll-free hotlines that people can call to talk to someone and seek assistance, as well as local resource information.

If during the study you are concerned that a participant intends to harm herself or others, then mandatory reporting procedures need to be followed on completion of the appointment. Immediately inform the Project Coordinator and the Site PI, who will report the mandatory reporting incidents to the ethics committee and our project officer within 72 hours.

In these instances, please follow the following steps:

- As far as possible, complete the study appointment.
- Indicate to the person that they seem upset or anxious.
- If they are expressing a desire to end their life (suicide), explore further whether this is an expression of distress or whether they have a) had previous attempts, b) have a plan to end their life.
- If there is immediacy and a plan for suicide, remind the person of the limits of confidentiality as expressed in the consent form, and your duty to report.
- Follow the mandatory reporting procedures described below.
- Complete the referral and release form
- Call the the mental health nurse to make an immediate appointment or accompany the participant to the ER section of the healthcare facility.
- Provide the patients with a copy of the referral letter in an envelope and keep one in the CONTACTS folder.
- Provide the patient with a copy of our resource guide for additional services.
- Follow the reporting procedures in Chapter 7- complete an incident report form and immediately send to the Project Coordinator and Site PI who will both keep copies on file.

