6.2.1.2. Procedure: IMMEDIATE RISK

If you assess that the participant is at **immediate risk** to herself, read the following script to the participant:

Script: Risk of participant suicide or self-injury (immediate danger of harm)

Team member reads:

"When you agreed to participate in this study, I promised that I would tell someone what you told me only if it was necessary to protect you or other people. You told me earlier that you were thinking of harming yourself. I suggest we contact an organization called LifeLine or SADAG and let them know so they can talk to you about how you feel. LifeLine and SADAG offers counseling. You can discuss your problem with one of their counsellors and they may be able to help you. Do you want to call them, or should I call them for you?"

Willing participant:

- If the participant agrees to contact Lifeline or SADAG, use the project phone to make the call for the participant, hand them the phone and go to another room to give them privacy during the call.
- If the participant asks you to make the call on their behalf, use the project phone to make the call for the participant, hand the phone to the participant and go to another room to give them privacy in the call.

Unwilling participant

- If the participant is unwilling to contact the crisis hotline and doesn't want you to contact them, then you should immediately contact the Project Coordinator/Site PI, who can assess the situation (e.g., determine reasons why the participant is unwilling to contact the hotline so these issues can be addressed) and who can contact one of the psychologists in the investigative team for further inputs.

- You can also contact the family physician and/or mental health nurse at the facility for their guidance.
- In the meantime, do not leave the participant by herself nor let them leave on their own, as they pose a risk to themselves.
- Ask the participant if she has a close family member or friend who can come to sit with them until you receive clear instructions about what to do.
- If the participant remains unwilling to contact the hotline, provide the participant with the referral guide as well as the counselling hotline numbers.
- Make sure you document who you spoke to, and the advice provided on the incident form (see Chapter 7)

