Social Harm	
1) Any untoward social occurrences that happen to a participant as a result of their participation in the study, or
 
2) any untoward social occurrences that happen to a community, or groups or individuals within a community, as a result of implementation of the study intervention
	Participants provide confidential information and if this information is leaked it can have detrimental effects	
Reporting to: Project Coordinator Senior Management: PI & Site PI

Protocol Deviation	Protocol non-adherence/violations (the research project's processes not being followed) leading to individual incidents, trends or omissions that result in significant added risk to the participant, non-adherence to significant protocol requirements and significant non-adherence to GCP.	
-Enrollment of an ineligible patient.
 
-Informed consent not obtained prior to performing protocol-specified procedures.
 
-Protocol-specified procedures not followed.
 
-Breach of participant confidentiality
	
Reporting to: Project Coordinator Senior Management: PI & Site PI
 
All Co-Investigators SAMRC Research Ethics Committee NIH Project Officer

Critical Events			
Unanticipated Problems	Any incident, experience or outcomes that is unexpected, has reasonable possibility of being related to a subject's participation in the research and suggests that the research places participants or others at	
-Loss of a computer/tablet that contains participants' private identifiable information.
 
-Participant experiences physical violence (e.g., domestic) as a result
	
Reporting to: Project Coordinator Senior Management: PI & Site PI

	greater risk of harm than previously known or recognized.	of participating in a research study. -Unintentional disclosure of family member's or partner's health status due to participation in the research	

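### The confidentiality assurance at screening (Protocol 5.2) states no exception, although the same screening turns on suicidality and the manual elsewhere states exceptions and makes some disclosures reportable

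*Protocol*

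**What the plan says.** Protocol 5.2 (Screening) acknowledges that the screener asks for sensitive information and has the fieldworker "Reassure them that their identity will never be linked to their responses and that their responses are only used for research purposes". It then adds: "Always remind individuals that their answers will be kept strictly confidential". Neither sentence carries a condition.

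The eligibility table in 5.2 excludes women who report suicidal thoughts now or an attempt in the previous month. The text after the table says that these women, and those with serious medical problems threatening the pregnancy, "will not be eligible and will be provided with necessary referrals".

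Other sections describe confidentiality differently:

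- 5.3 (Baseline Assessment) has staff remind the woman of confidentiality, except where she indicates a wish to harm herself or someone else.
- 6.1.2 says: "Remember that we have made it clear in the consent form that there are exceptions to our promise of confidentiality". It names intent to harm oneself or others and continuing child abuse or neglect, and describes a duty to report to the authorities.
- 6.2 makes reporting compulsory in three situations: suicidal intent, intent to hurt others, and child abuse or neglect.
- 6.2.1.2 gives a script for immediate risk that begins: "When you agreed to participate in this study, I promised that I would tell someone what you told me only if it was necessary".

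On the order of steps, 2.2.2 lists fieldworker duties as "conducting screening to identify potential patients who are eligible to participate in the study, consenting eligible patients and enrolling them in the study". The end of 5.2 places collection of contact details and scheduling of baseline after consent.

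**The concern.** Screening is where a woman's suicidality is first elicited, and it is also the step at which she is told that nothing she says will be linked to her or used outside research. The manual does not keep to that in every case. A woman may disclose on the strength of an assurance that the same manual qualifies later.

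Two things are at stake. Section 3.1.1 lists a right to accurate representation, which requires that what participants are told about the study be fully accurate. And a fieldworker who follows 5.2 to the letter, then hears something that Chapter 6 makes reportable, holds two instructions that do not agree.

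**Working it through.** No arithmetic applies. The check sets the screening assurance beside the manual's own uses of a screening answer. The SAP does not touch the point.

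**Step 1: is the assurance conditional anywhere in 5.2?** No. Both sentences are unqualified. The reminder in 5.3 does carry a harm exception, so suitable wording already exists in the manual but is missing from the section that asks about suicidality.

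**Step 2: does each part of the assurance hold, case by case?**

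- *Answers raise no safety issue.* Nothing in Chapter 6 is engaged, and this conflict does not arise.
- *The woman reports suicidal thoughts or a recent attempt, without expressing a wish to injure or kill herself.* She is excluded and referred. Referral acts on her answer for her care, so the claim of research use only is inaccurate. If the referral form of Chapter 6 is used, it is filed under 5.6.2 with identifying documents, which ties the matter to her name. Section 5.2 does not say whether that form is used at screening.
- *The answer meets a trigger in 6.2.* Reporting becomes compulsory. Action under 6.2.1.2 may involve the coordinator, the site investigator, a psychologist, or the facility's physician or mental health nurse, and 6.1.2 speaks of reporting to authorities. None of this can be done for an individual without connecting her to what she said. All parts of the assurance then fail.

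**Step 3: does Chapter 6 reach a woman who is only being screened?** Chapter 6 speaks of participants and does not define the term. Section 5.2.1 uses it for women still in screening ("Provide participant with a urine cup to collect a urine sample as part of the screening process"), which suggests a broad meaning but does not settle it. If Chapter 6 applies, the third case arises as described. If it does not, the manual gives no procedure for her beyond referral, and the second case remains.

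**Step 4: has she been told the limits by another route?** Section 6.1.2 relies on the consent form, and 6.2.1.1 and 6.2.1.2 rely on the consent form or on an earlier conditional promise. The order in 2.2.2 and 5.2 suggests that consent follows a finding of eligibility. A woman excluded at screening may then never see that form, and the 6.2.1.2 script would describe an agreement she had not made. This is an inference, because consent pages are not in the public file.

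**Step 5: does the conflict depend on Step 4?** No. Even if a separate screening consent states the limits, 5.2 still tells staff to say something that 5.3, 6.1.2 and 6.2 contradict.

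**The case against.** The strongest reply has five parts.

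1. *Consent material is missing from the file.* Section 5.1 promises a fuller account of the consent process that is not visible, and consent pages were removed. A screening consent may exist. This stands: no conclusion can rest on consent coming after screening.
2. *Women excluded for suicidality are not abandoned.* They are referred. Under 6.1.1 a call to an agency is made with permission, and the script in 6.2.1.2 first offers a hotline call. This stands. A reader might infer that staff must either break their word or do nothing, and the documents do not support so stark a choice.
3. *The trigger is narrower than the screening item.* Section 6.2 refers to a wish to hurt or kill oneself, and the eligibility item covers suicidal thoughts generally. This stands, so compulsory reporting concerns a subset of excluded women. Referral, however, is stated for all of them.
4. *Chapter 6 is written for participants.* Its silence on screened women is a gap in scope, not proof that its script is wrong. This stands, and reconciliation is the proper request.
5. *The screener is filed among non-identifying forms (5.6.1), and contact details are collected only after consent.* The claim about identity can be read as describing how the record is kept. That softens the first half of the sentence. It does not rescue the claim of research use only or supply the missing exception.

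A reader might also infer that the urine EtG test at screening is itself a protocol deviation, since the table in 7.2 lists "Informed consent not obtained prior to performing protocol-specified procedures". The documents do not support this. That phrase is an example, while the table's definition concerns departures from the project's own processes. Collecting urine at screening follows 5.2.1 as written, and whether consent precedes it cannot be seen.

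**Conclusion.** The concern holds as an internal contradiction in the manual. The unconditional assurance in 5.2 does not agree with the exception in 5.3, the limits in 6.1.2, the compulsory reporting in 6.2, or the referral in 5.2 itself. It is inaccurate for women referred on their suicidality answer and untrue when a screening answer meets a 6.2 trigger.

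The assurance is given to every woman screened. The manual plans 60 enrolments (30 pregnant, 30 post-partum) but gives no number to be screened and no expected rate of suicidality, so the number misled cannot be estimated. The disposition table in 5.2 has no specific code for exclusion on this ground, so those exclusions could not be counted separately from it afterwards either.

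The conclusion rests on the wording of 5.2 and on suicidality being established at screening, as the eligibility table requires. Applying the reporting trigger to women who are not enrolled also assumes that Chapter 6 covers them. A reader might go further and conclude that every woman excluded for suicidality leaves without having been told the limits. That would need consent to follow screening with no separate screening consent, which the public file cannot confirm.

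This is a matter of participant protection and accurate information. It should be corrected, but it changes no estimate, test or sample size.

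**What to change.** In 5.2, replace the never-linked and research-only wording with a confidentiality statement that carries the exceptions already in the manual, given before the screener questions. Section 5.3 names only harm to self or others, while 6.1.2 also names child abuse and neglect, so the statement should cover both. The reminder about strict confidentiality should be made subject to the same exceptions.

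Reconcile 5.2 with 6.1.2 to 6.2.1.2 on whether Chapter 6 covers women who are screened but not enrolled, and on whether the 6.2.1.2 script, which presumes agreement to participate, is meant for them. How such women should be managed is for the investigators and the ethics committee.

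The cost is a short text change, an ethics amendment, a briefing for fieldworkers and translation, since the screener exists in English, IsiXhosa and Afrikaans. The real downside is that some women may disclose less once the limits are stated, which could make the suicidality exclusion less complete.
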